After randomization, sedating antihistamines (e.g. diphenhydramine, hydroxyzine) can be used as needed for insomnia; however, patients must be able to discontinue them during the screening phase and must refrain from their use during the week of baseline data collection preceding Visit 2. The use of sedating anti-histamines after randomization should always be under the direction of the Investigator, and such use should be minimized to no more than a few nights in a row, followed by attempts to refrain from use.

The use of melatonin, ramelteon, and valerian root is not restricted.

New medications that are deemed required, in the opinion of the Principal Investigator or another physician, will be allowed, including medications needed to treat adverse events. If there is a requirement for acute opioids, corticosteroids, or other treatments that could confound the evaluation of pain at critical times (defined as the week prior to Clinic Visits 2, 3, 4, 5 or 6), the Investigator may consult with the Medical Monitor to potentially delay the study visit until the medication is no longer needed. At a minimum, no opioid/narcotic should have been utilized within 2 days of a study visit, and ideally there will have been no usage during the 7 days prior to any visit since important efficacy data will be collected on the diary during the week leading up to each clinic visit.

Statistical methods:

Efficacy Analyses:

The primary efficacy parameter will be the contrast between TNX-102 SL and placebo in the weekly mean change from baseline pain score at the endpoint visit. The weekly pain score will be based on the weekly average of the daily diary patient self-reported 24-hour recall average pain severity scores using an 11-point (0-10) NRS.

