- ^d Clinical laboratory tests (hematology and serum biochemistry) will be performed at Screening and Week 14/ET. For patients where a telephone visit is being conducted for Week 14/ET, the laboratory tests will not be required. TSH will be tested at Screening only. Optional HCV/HBsAg testing may be performed at Screening at the discretion of the Investigator or Sponsor. Medical Monitor approval is required prior to testing.
- ^e A serum pregnancy test will be performed at Screening, followed by in-clinic urine pregnancy tests at Baseline, Week 2, Week 6, Week 10 and Week 14/ET for women of child-bearing potential. For patients where a telephone visit is being conducted, the urine pregnancy test will be performed at home by patient for women of child-bearing potential.
- ^f Vital signs (oral temperature, weight and sitting blood pressure and heart rate [obtained after resting for 5 minutes in a sitting position]) will be measured at each visit. Height will be measured at Screening only. For patients where a telephone visit is being conducted, the vital signs will not be required.
- ^g A 12-lead electrocardiogram will be obtained at Screening. All electrocardiograms will be performed and interpreted locally.
- ^h Clinic staff members will train the patient on how to take the study drug and how to complete the diary. Patients will be asked to complete their diary every evening. Diary completion will start on the evening of Visit 1 and continue through Week 14. Diary responses will be monitored during the study.
- ⁱ The study drug will be dispensed to patients at Baseline on Day 1 (following randomization) and at Weeks 2, 6, and 10. One bottle will be dispensed on Day 1 and two bottles will be dispensed at Weeks 2, 6 and 10. For patients where a telephone visit is being conducted, the study drug will be mailed via courier to their home. Patients will be instructed to take one tablet of study drug sublingually every evening at bedtime for 2 weeks starting the evening of Day 1, and then 2 tablets sublingually every evening from Week 2 to Week 14.
- ^j Patients will assess their average daily pain over the last 24 hours every evening using an 11-point (0-10) numerical rating scale. Patients should be instructed to complete their diary responses in the evening, but before taking their bedtime dose of study drug. The 24-hour recall interval will assess the previous night's sleep and symptoms of pain since bedtime the previous night.

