8.2. Patient Inclusion Criteria

Patients enrolled in this study will be volunteer patients. Eligible patients must meet all of the following inclusion criteria during the screening period:

1. The patient is male or female 18 to 65 years of age, inclusive.
2. The patient has a diagnosis of primary FM as defined by the 2016 Revisions to the 2010/2011 fibromyalgia diagnostic criteria (American College of Rheumatology Preliminary Diagnostic Criteria), which includes all of the following:
 - a. Generalized pain, defined as pain in at least 4 of 5 regions
 - b. Symptoms have been present at a similar level for at least 3 months; and
 - c. Widespread pain index (WPI) ≥ 7 and symptom severity scale (SSS) score ≥ 5 ; OR WPI between 4-6 and SSS scale score ≥ 9 ; and
 - d. The patient does not have another disorder that would otherwise explain his/her pain.
3. The in-clinic 7-day recall NRS average daily pain intensity score at Screening Visit must be ≥ 4 and ≤ 9 . Exceptions are only possible with Medical Monitor approval.
4. If female, is either not of childbearing potential (defined as postmenopausal for at least 1 year or surgically sterile [e.g., bilateral tubal ligation, bilateral oophorectomy, or hysterectomy]) or will be practicing one of the following methods of birth control throughout the study:
 - a. Hormonal methods such as oral, implantable, injectable, or transdermal contraceptives for a minimum of one full cycle (based on the patient's usual menstrual cycle period) before study drug administration;
 - b. Intrauterine device (IUD);
 - c. Double-barrier method (condoms, sponge, diaphragm, or vaginal ring with spermicidal jelly or cream);
 - d. Partners of vasectomized males in stable relationships;
 - e. Females involved in stable same sex relationships;
 - f. Female patients practicing abstinence may have the birth control requirement waived only with Medical Monitor approval.
5. Patients currently receiving non-exclusionary pharmacologic treatment for depression should have been clinically stable for at least 3 months prior to randomization, and on stable doses of the antidepressant regimen during this 3-month time frame.
6. The patient must be willing and able to withdraw from the following therapies for the duration of the study: duloxetine, milnacipran, pregabalin, gabapentin, tramadol, tapentadol,

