New medications that are deemed required, in the opinion of the Principal Investigator or another physician, will be allowed, including medications needed to treat adverse events. After randomization, if there is a requirement for treatment with an acute opioid or other treatment that may confound the evaluation of pain at critical times during the study (defined as the week prior to Visits 3, 4, 5 or 6), the Investigator may consult with the Medical Monitor to potentially delay the study visit until the medication is no longer needed. At a minimum, no opioid/narcotic should have been utilized within 2 days of a study visit, and ideally there will have been no usage during the 7 days prior to these visits. While it is understood that opioid usage will occasionally be necessary and unavoidable, it could have consequences on the patient's data.

Similarly, if there is a requirement for acute, short-term opioid usage during the screening phase, the start of the 7-day run-in phase should be delayed to ensure at least 2 days between the last opioid dose and the beginning of the 7-day run-in phase. In other words, there may be some circumstances when the unexpected requirement for short-term opioid usage, specifically due to an *acute* medical, dental or surgical condition, does not require the full 21-day washout. This provision only applies to *acute* pain conditions – not to opioid usage due to a flare in patient's FM or other chronic pain condition. Any requirement for acute opioid usage during the screening phase should be brought to the attention of the Medical Monitor to ensure adequate washout prior to randomization.

Patients should refrain from drinking grapefruit juice or eating grapefruit during the study due to its ability to inhibit CYP3A4 activity. Aside from this restriction, there are no other food or fluid restrictions in this study except for the instructions pertaining to dosing ([Section 10.2](#)).

Patients using teeth-whitening products such as whitening strips or prescription whitening products must agree to discontinue their use from the day of randomization until the end of their study participation.

Any concomitant medications or other treatments must be recorded in the patient's medical record and case report form along with the dose and dates of treatment.

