4.4.2 Intermittent Missing Data

Intermittent missing daily data will not be imputed and weekly averages will be calculated using available values, even if only a single value is available for a week. Intermittent missing data (weekly averages and/or in-clinic assessments) occurring prior to discontinuing use of study drug is assumed to be missing at random, and analyses have been chosen to mitigate the impact of these missing data ([Section 10.1](#)).

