10.1.3 Sensitivity Analyses

Four sensitivity analyses will be performed:

For the first, pain scores will be censored on the day(s) on which an opioid is utilized. If the subject utilizes an opioid for any indication, then the pain score on each impacted day will be replaced by the score obtained on the day immediately prior to the first day of opioid use (and until the opioid is no longer used). This will be done prior to the weekly averaging, and all other calculations will be performed as described in the primary. This will investigate whether use of concomitant opioids influences the interpretation of study results.

For the second, subjects that discontinue due to “withdrawal of consent” or “investigator decision” will be grouped with the LOE and AE dropouts when performing the multiple imputation procedure. This analysis will investigate whether the categorization of these reasons for dropout influences the interpretation of study results.

For the third, ALL subjects that discontinue will be grouped with the LOE and AE dropouts when performing the multiple imputation procedure. This analysis will sample from the baseline distribution of all dropouts and will investigate whether treating dropouts as treatment failures (on average) influences the interpretation of study results.

Finally, a tipping point analysis will be performed on the values for the primary analysis. A shift parameter will be applied to the active treatment arm starting at .25 and increasing in increments of .25 through either 5 or when the outcome is no longer significant. This will only be performed if the primary analysis is significant. This will test the overall robustness of the

primary analysis.

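### The opioid sensitivity analysis replaces diary scores only on days of use, so it keeps the next evening's 24-hour-recall entry, which can still be affected

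*SAP*

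**What the plan says.** SAP 10.1.3 plans four sensitivity analyses. Two regroup reasons for dropout and one is a tipping-point analysis. The first is the only efficacy analysis that deals with co-treatment: "pain scores will be censored on the day(s) on which an opioid is utilized". Whatever the indication, each such score is "replaced by the score obtained on the day immediately prior to the first day of opioid use", and the replacement ends when opioid use ends. This is done before weekly averaging; all later steps follow the primary analysis. The stated aim is to learn whether concomitant opioids change how the results should be read.

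The diary timing is in the Protocol Synopsis, Table 2, footnote j: "Patients should be instructed to complete their diary responses in the evening, but before taking their bedtime dose of study drug". The same footnote makes the recall reach back to the previous bedtime. Protocol 9.1 asks for the dose and dates of concomitant medication; it does not mention clock time.

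The documents name an interval after opioid use in two settings. For acute opioid need during screening, Protocol 9.1 delays the run-in to "ensure at least 2 days between the last opioid dose and the beginning of the 7-day run-in phase". SAP 4.4.1 and Protocol 9.1 also set a minimum of 2 opioid-free days before a study visit, and ideally 7.

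For gaps in the diary, SAP 4.4.2 states: "Intermittent missing daily data will not be imputed and weekly averages will be calculated using available values".

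**The concern.** A score that looks back over 24 hours does not line up with a rule defined by the calendar day of use. The entry made on the evening after the last opioid day can describe time under the opioid, and the analysis treats it as clean. The replacement value is also thin: one day's score stands in for a whole course of use, and the rule gives nothing to insert when that day has no entry.

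What is at stake is the meaning of a reassuring result. If the analysis still contains affected scores, agreement with the primary result does not fully show that opioids made no difference.

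**Working it through.** The documents give no figure for this point, so there is none to reproduce. The check sets the rule against the diary and then sizes the gap under stated assumptions.

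**Step 1. Rule against diary.** Take a single day of use, day d.

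| Opioid taken | Entry on day d | Entry on day d+1 |
|---|---|---|
| Before the evening entry | Affected; rightly replaced | Can still be affected; kept |
| After the evening entry | Unaffected; replaced anyway | Affected; kept |

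In a longer course only the two ends matter, because the days between are replaced in either case. Since only dates are requested, the two rows may not be separable in the data. A rule that runs through day d+1 covers both.

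**Step 2. Share of affected entries kept.** Let k be the days of use and L the further affected entries after the last use. L = 1 reflects the recall window. L = 2 is an assumption that borrows the trial's 2-day gap. Share kept = L / (k + L).

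- k = 1: 1/2 = 50% for L = 1; 2/3 = 67% for L = 2.
- k = 3: 1/4 = 25% for L = 1; 2/5 = 40% for L = 2.

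**Step 3. Shift in one patient's weekly mean.** Let x be the opioid effect on a daily score, assumed to be 1 to 3 NRS points. With seven entries in the week, shift = x × L / 7.

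- L = 1: 1/7 = 0.14 to 3/7 = 0.43.
- L = 2: 2/7 = 0.29 to 6/7 = 0.86.

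**Step 4. Residual in the treatment contrast.** Let δ be the difference between arms in the proportion of patients with such days in Week 14, assumed to be 0.02 to 0.10. With the same x and L in both arms, residual = δ × x × L / 7.

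- Smallest: 0.02 × 1 × 1 / 7 = 0.003.
- Largest: 0.10 × 3 × 2 / 7 = 0.09.

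If use is equal in the two arms, the residual cancels. The documents do not say how many patients would be affected.

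**Step 5. The replacement value.** If opioid use fills a week, that week's value is a single daily score. Relative to a 7-day mean its between-subject variance is 7 / (1 + 6ρ), where ρ is the day-to-day correlation (assumed).

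- ρ = 0.5: 7/4 = 1.75, an SD ratio of √1.75 = 1.32.
- ρ = 0.8: 7/5.8 = 1.21, an SD ratio of √1.21 = 1.10.

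The carried value enters as if observed, so the multiple imputation adds no uncertainty for it. A missing score on the prior day is a case the SAP itself foresees, since 4.4.2 and 8.2.1 accept weeks with a single entry, yet 10.1.3 has no rule for it.

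**The case against.** The strongest reply is that this is one sensitivity analysis out of four, that chronic opioid users are screened out, and that any residual in the contrast is small. That stands. So do several limits on how far the point can be pushed.

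- A reader might infer that the rule generally picks the wrong days. It does not: when the opioid precedes the evening entry, the day of use is the right day to replace, and the fault is only that the following entry is left in.
- A reader might take the 2-day gap as the trial's own carry-over period for diary scores. The documents use it to schedule visits and as a minimum before the run-in. Using it as a statistical lag is a choice.
- A reader might see a conflict with SAP 4.4.2. That section concerns values that are missing; 10.1.3 replaces values that were observed.
- A reader might quote a 2.6-fold SD for a fully replaced week. That is √7 and needs independent days, which is unlikely for chronic pain scores.
- A reader might object that other co-treatments are ignored. The Protocol Synopsis does list "acute opioids, corticosteroids, or other treatments that could confound the evaluation of pain at critical times", and the SAP flags only opioids. But the estimand in SAP 10.1.1 follows the randomised assignment, so keeping scores recorded under a newly started drug is consistent with it. Concomitant medications are also tabulated by arm (SAP 12.1).
- A reader might call Protocol 9.1 ("New medications that are deemed required, in the opinion of the Principal Investigator or another physician, will be allowed") and Inclusion Criterion 6 ("The patient must be willing and able to withdraw from the following therapies for the duration of the study") contradictory. One concerns later medical need and the other willingness at entry; they can coexist.

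Setting scores to missing has a cost too. Some weeks will rest on few entries, and empty weeks will rely on an untestable missing-at-random assumption for patients still on treatment. None of this removes the core point: the next diary entry is kept, and a missing prior-day score has no rule.

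**Conclusion.** The concern holds in limited form. The analysis stops at the last day of use although the next 24-hour-recall entry can still be affected. It may replace an unaffected first-day score, and it carries one prior-day score over the whole course with no fallback. For a one-day course it keeps 1 of 2 affected entries (L = 1), or 2 of 3 if a 2-day lag is assumed.

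The size is modest: 0.14 to 0.86 NRS points in an affected patient's weekly mean, and about 0.003 to 0.09 in the contrast. Both ranges rest on an assumed effect of 1 to 3 points on every retained day; the second also assumes a 2 to 10 percentage-point imbalance in Week 14 use. The primary analysis and its estimand are not called into question. The check simply does not fully answer the question it was written to answer, and the remedy is cheap.

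**What to change.** In SAP 10.1.3:

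- Define the affected period as the first day of opioid use through at least the diary day after the last use. Two days is an option, to align with the gap in SAP 4.4.1 and Protocol 9.1.
- Set scores in that period to missing, average the remaining days as in 4.4.2, and let the imputation in 8.1.3 handle empty weeks.
- Fix each patient's Week 14 anchor under 8.2.1 before removing any score. That section works back to the last non-missing day, so censoring first would move the window.
- If the carry-forward is kept instead, state which score is used when the prior day has no entry.

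Optionally, add a supplementary analysis that applies the same handling to newly started systemic corticosteroids and the Inclusion Criterion 6 drugs, from a list fixed at the blinded medication review. It would address a different, hypothetical question and should be labelled so; the primary estimand stays as it is. Exclusion Criterion 13 is too broad to serve as that list, since it includes stimulants, weight-loss agents and strong CYP3A4 inhibitors.

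The cost is a few lines of SAP text, a little programming, and slightly more missing daily data in one sensitivity analysis.

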10.2 Secondary Efficacy Analyses

Secondary efficacy analyses will be based on the ITT population only.

Continuous Endpoints

For the purposes of possible label claims and reported p-values entered into the multiplicity algorithm, an approach identical to the primary analysis will be used for all continuous outcomes. See [Section 8.1.3](#) for the imputation algorithm and [Section 10.1.2](#) for the analysis approach.

Outcomes using these analyses will include:

- Change from baseline in the FIQR symptoms domain score
- Change from baseline in the FIQR function domain score
- Change from baseline in the PROMIS score for sleep disturbance
- Change from baseline in the PROMIS score for fatigue
- Change from baseline in the weekly average of the daily diary assessment of sleep quality.

For each, all time points will be summarized, but the primary time point of interest is Week 14. Time points other than Week 14 are considered exploratory. The estimand for each is identical to the primary, substituting for the endpoint in question.

For the sleep quality assessment collected via a daily subject diary, the baseline score and the weekly scores for each subject will be calculated as the weekly average score based on the mean of the scores recorded for that study week ([Section 8.2.2](#)).

This will be repeated on the outcomes above, but using observed data only without imputation.

Categorical Endpoints

A categorical analysis of PGIC will be performed using a logistic regression model for each week with effects for treatment and investigative site. If the model does not converge, site will be removed from the model. Subjects with results of “very much improved” or “much improved” (defined as responders) will be compared to all other categories (defined as non-responders). Subjects with missing data will be considered non-responders. In addition, odds ratios and corresponding 95% CI intervals for being “very much improved” or “much improved” versus all other categories will be presented. A summary of frequency counts for PGIC responses for each time point will be presented; Week 14 is of primary interest and all other time points are considered exploratory.

